Cerebrolysin as an Early Add-on to Reperfusion Therapy: Risk of Hemorrhagic Transformation after Ischemic Stroke (CEREHETIS). A Prospective, Randomized, Active-Control, Multicenter Pilot Study

Clinical Trial Protocol

Date: 30 April 2018

PROTOCOL SYNOPSYS

Sponsor None

Final Product Cerebrolysin

Active Ingredient Cerebrolysin concentrate

Clinical Trial Title

Cerebrolysin as an Early Add-on to Reperfusion Therapy: Risk of Hemorrhagic Transformation after Ischemic Stroke (CEREHETIS). A Prospective, Randomized, Active-Control, Multicenter Pilot Study

Primary Investigator

[name]

Clinical Trial Centers

- 1. Interregional Clinical Diagnostic Center (Kazan, Russia), tertiary stroke center
- 2. Municipal Clinical Hospital #7 (Kazan, Russia), primary stroke center
- 3. Federal University Hospital (Kazan, Russia), primary stroke center
- 4. Perm Territorial Clinical Hospital (Perm, Russia), primary stroke center
- 5. Emergency Medical Center (Naberezhnye Chelny, Russia), primary stroke center
- 6. Leninogorsk District Hospital (Leninogorsk, Russia), primary stroke center
- 7. Nizhnekamsk District Hospital (Nizhnekamsk, Russia), primary stroke center
- 8. Arsk District Hospital (Arsk, Russia), primary stroke center

Clinical Trial Schedule

First subject's first visit: April 2018 Last subject's last visit: August 2020 (extension possible) Study report completion: September 2020

Clinical Trial Phase

IIIb

Goals of the Study

Primary objectives:

To test the hypothesis that the patients in the Cerebrolysin group would achieve reduced incidence of intracranial haemorrhagic events compared to the patients randomised to the control group

Secondary objectives:

To test the hypothesis that more patients in the Cerebrolysin group would achieve short- (day 14) and long-term (day 90) favorable functional outcome after stroke.

To evaluate hypothesis that the use of Cerebrolysin with thrombolytic therapy would be safe.

Additional objectives:

To test the hypothesis that Cerebrolysin would ameliorate ischemic injury to the brain tissue (neuroprotective effect) and stabilize blood brain barrier (BBB) permeability in stroke patients.

Methodology

A prospective, randomized, open-label, active control, multicenter, parallel-group phase IIIb pilot study.

Sample Size Calculation

Sample size calculation was performed by means of power analysis for matched case-control studies using STATA v.14.2.

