Additional Inclusion Criteria for Advanced Brain Imaging:

- No contraindications to magnetic resonance imaging (MRI) and computed tomography (CT) perfusion (CTP) study
- Stroke in the middle cerebral artery territory with a minimum diffusion-weighted imaging (DWI) lesion diameter of 20 mm on admission

Study product, dose and method of administration:

Both groups would receive a standard dose of 0.9 mg/kg recombinant tissue plasminogen activator (rtPA; alteplase) administered by IV infusion within 4.5 h after symptom onset. In addition, measures of standard care for stroke patients would be applied for both groups. Patients in the Cerebrolysin group would additionally receive 30 mL of Cerebrolysin diluted in 100 mL of normal saline administered intravenously through a separate IV line over 20 min. No treatment with other neuroprotective agents would be allowed.

Length of the Study:

Cerebrolysin treatment would be initiated simultaneously with IVT and continued once daily for 14 consecutive days. A follow-up period would be 90 days for each patient. The visits would be scheduled as follows: screening (on admission), in 24 h (visit 1), on day 7, 14, and 90 (visit 2, 3, and 4, respectively).

Endpoint evaluation:

Primary endpoint evaluation:

The study primary endpoints would be any and symptomatic HT verified on a follow-up CT scan. Symptomatic HT would be defined according to the ECASS III trial: any apparently extravascular blood in the brain or within the cranium that is associated with clinical deterioration, as defined by an increase of 4 points or more in the score on the NIHSS, or that lead to death and that is identified as the predominant cause of the neurologic deterioration.

Secondary endpoint evaluation:

Secondary endpoints would be the functional outcome measured with the National Institutes of Health Stroke Scale (NIHSS) and modified Rankin scale (mRS) as well as drug safety.

Favorable functional outcome would be defined as the mRS score of ≤ 2 at V4 (day 90).

The NIHSS score at V3 (day 14) would be considered as a marker of short-term neurological recovery.

Patients in both arms would be monitored for any adverse events (AE) at V1-3, including changes in vital signs, general and neurological condition, electrocardiogram, and routine laboratory tests (liver and kidney function tests, complete blood count).

Additional evaluation (advanced brain imaging):

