3. CLINICAL STUDY DESIGN

The study is designed to investigate efficacy of cerebrolysin 30 mL for patients with ischemic stroke during IV TLT and standard baseline therapy and early neurorehabilitation.

Therefore, the study design provides for two study groups:

Study group 1 (Cerebrolysin): 30 mL of cerebrolysin in 100.0 mL of 0.9 % NaCl during IVT, baseline therapy, early neurorehabilitation according to standards

Study group 2 (Control): IVT, baseline therapy, early neurorehabilitation according to standards

The clinical study will be carried out in patients with ischemic stroke meeting IVT inclusion and exclusion criteria (Clinical Guideline for Thrombolytic Therapy During Ischemic Stroke (National Clinical Guidelines:

http://193.232.7.120/feml/clinical_ref/0001410674S/HTML/)

The diagnosis of ischemic stroke and its localisation will be determined clinically based on neuroimaging findings (TOAST criteria).

The clinical study stipulates for follow-up period of 90 days, with 4 scheduled visits for clinical assessment at the following time points: screening (at admission), in 24 hours, on day 7, 14, and day 90.

The clinical study is expected to begin in April 2018 (first patient enrollment) and to end (final study report) by September 2020.

The clinical study is expected to be performed from 2018 till 2020.

Patient visits	Screening	Visit 1	Visit 2	Visit 3	Visit 4
Time since treatment initiation	Admission	24 hours after initiation of therapy	Day 7 after treatment initiation	Day 14 after treatment initiation	Day 90 after treatment initiation
Baseline patient information (demographic data, medical history)	+				
Inclusion/exclusion criteria review	+				
Randomisation, number assignment	+				
Non-contrast CT of the brain	+	+	+	+	
CTP* (PS)				+	
MRI* of the brain (DWI, FLAIR, 3D TOF)	+				
MRI* of the brain (DWI, DTI, 3D TOF, ROI)		+			
MRI* of the brain (DTI)				+	
Assessment of neurological impairment using to the NIHSS scale	+	+	+	+	
Assessment of disabilities using the Rankin scale (attachment)	+			+	+
Assessment of vital functions (BP, RR, pulse, T)	+			+	
Haematology	+			+	
Serum biochemistry	+			+	
CRP		+			
ECG	+				
Assessment of the presence and severity of adverse events		+	+	+	

Schedule of the clinical study procedures

* For patients, eligible for advanced brain imaging at the tertiary stroke center.

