The treatment period will be 14 days. During this period which will always begin 45-270 minutes after stroke onset the patient will receive daily intravenous dose of the study product. The treatment will be assigned by randomization. In 24 hours (visit 1), on days 7 (visit 2), 14 (visit 3) of the treatment period further evaluation procedures will be made according to table "Schedule of the Clinical Study Procedures". Throughout the clinical study all adverse events regardless of their association with cerebrolysin will be collected and recorded in standardised adverse event and serious adverse event forms. Serious adverse events are defined as any medically unfavourable event developing after administration of any dose of the product and resulting in long-term or expressed disability/incapacity. Diagnosis rather than the signs, symptoms and/or other clinical information should be recorded as possible. Severity of each adverse event should be qualified as mild, moderate or severe. The events are evaluated medically including testing and referral to medical specialists. All the current requirements of local regulatory authorities concerning notification of regulatory authorities and local ethics committee on serious adverse events will be followed.

In case a significant adverse event is detected, discontinuation or planned continuation of the study therapy should be discussed immediately. The key factor in this discussion should be the severity of the adverse event and the probability that this adverse event or its exacerbation may be induced by cerebrolysin. The study therapy should be suspended if the patient reports an adverse event which, according to the investigator, may result in discontinuation of further of therapy or if the patient or his/her relatives apply for discontinuation of further therapy.

At the final visit (visit 4, day 90), Rankin scale rating is scheduled.

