1. SAFETY DATA

Safety data should include AEs, vital signs and laboratory tests including haematology, serum chemistry, and urinalysis.

All the AEs developing after signing informed consent should be recorded regardless of whether they are considered as related or unrelated to the study product. At each visit, the investigator should detect AEs and evaluate them. AEs should be monitored until reduction of intensity, classification as medically stable or until loss to follow-up.

AEs should be recorded directly in CRF. Analysis will be performed in accordance with statistical analysis plan.

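### The protocol gives two incompatible adverse-event collection windows, and no scheduled assessment asks about new events on days 15 to 90

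*Protocol*

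**What the plan says.** Safety is a secondary objective with no time frame attached: "To evaluate hypothesis that the use of Cerebrolysin with thrombolytic therapy would be safe" (Synopsis, Goals of the Study). Treatment is "continued once daily for 14 consecutive days", and each patient is followed for 90 days. Visits 1 to 4 fall at 24 hours, day 7, day 14 and day 90 (Synopsis, Length of the Study).

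Two sets of statements then describe when adverse events are collected.

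**To day 14.**
- Synopsis, Secondary endpoint evaluation: "Patients in both arms would be monitored for any adverse events (AE) at V1-3".
- Clinical Study Design, section 3: the schedule row "Assessment of the presence and severity of adverse events" is marked at Visits 1, 2 and 3 and is blank at Visit 4. The only mark in the Visit 4 column is the Rankin scale.
- Clinical Study Design, section 6: "At the final visit (visit 4, day 90), Rankin scale rating is scheduled".

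**Whole study.**
- Clinical Study Design, section 6: "Throughout the clinical study all adverse events regardless of their association with cerebrolysin will be collected and recorded".
- Safety Evaluation, section 1: all events after consent are to be recorded, with no end date, and "At each visit, the investigator should detect AEs and evaluate them".
- Safety Evaluation, section 2: the definition of an adverse event covers changes at any phase of the study.

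**The concern.** Visit 4 is a scheduled visit, so an instruction to detect events at each visit cannot hold alongside a schedule that omits them at Visit 4. A centre that works from the schedule will not ask about new events after day 14. A centre that works from the safety sections will. Both would be following the protocol.

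What is at stake is how the safety comparison can be interpreted. There are eight centres, and section 4 of the design says that investigators and participants know the allocation. If late events reach the database only when someone volunteers them or an investigator thinks to record them, reporting may vary by centre and also by arm. The day 15 to 90 data would then be neither absent nor comparable, and a table pooling all recorded events would mix a systematically assessed period with one that was not.

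This cannot be left to the statistical analysis plan. It concerns data collection, and the synopsis says the detailed plan is to be written after study completion. By then, events that nobody asked about cannot be recovered reliably.

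**Working it through.** The protocol gives no figure for this point, so there is none to reproduce. The check compares the stated windows and measures the gap between them.

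**Inputs**
- Last visit with a scheduled adverse-event assessment: Visit 3, day 14 (synopsis and schedule).
- End of follow-up: day 90 (synopsis).
- Visit 4 content: Rankin rating only (schedule and section 6).
- Broader rules: section 6 of the design; Safety Evaluation, sections 1 and 2.

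**Length of each window**

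| Rule followed | Days covered by scheduled or required collection | Share of follow-up |
|---|---|---|
| Synopsis and schedule | 14 | 14/90 = 15.6% |
| Section 6 and Safety Evaluation | 90 | 90/90 = 100% |

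Gap: days 15 to 90 inclusive = 90 − 15 + 1 = 76 days, and 76/90 = 84.4%.

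**Can the two sets be read together?** One could try reading the schedule as the minimum of active questioning and the broader rules as a duty to record whatever else comes to light. That works for the throughout-the-study and any-phase wording. It fails for the instruction in Safety Evaluation, section 1, which requires active detection at each visit and so includes Visit 4. The conflict there is direct, and no text ranks one passage above another.

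**What reaches the record after day 14 in any case?**
- Death: Rankin grade 6 at day 90 (Efficacy Evaluation, section 1). The grade gives the fact of death, not its cause.
- Events already open at day 14: followed until they lessen, are medically stable, or the patient is lost (Safety Evaluation, section 1). New events are not covered by this.
- Withdrawals: reason, date and time go in the CRF, with monitoring to 90 days where possible (section 7 of the design). This reaches withdrawn patients only.
- New events in patients who remain in the study: to be recorded under the broader rules, but with no scheduled question to bring them out.

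The last line is the gap.

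**The case against.** The strongest reply is that the broader rules are binding text. A hospital readmission on day 30 or a death on day 40 meets the serious-event definition in Safety Evaluation, section 2, and must be recorded under that part of the protocol and under section 6 of the design, which also requires the local rules on notifying authorities and the ethics committee to be followed. Death is a listed reason for early withdrawal, so its date should enter the CRF. This stands. It rules out a stronger reading that a reader might infer: that late events leave no record, or that safety is answered for only 14 of the 90 days. That reading holds only if the synopsis and schedule override the safety sections, and no passage says they do.

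Second, an adverse-event window matched to 14 days of treatment can be a legitimate choice in an exploratory pilot. The objectives attach day 90 to functional outcome and give no time frame for safety. This also stands in principle, but the protocol nowhere says it made that choice, and three of its sections say otherwise.

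Third, 84% counts days, not events. The protocol gives no event rate after day 14, and haemorrhagic transformation, the main concern of the trial, is sought by CT at 24 hours, day 7 and day 14. This stands too: the figure measures the unassessed period and says nothing about how many events would be missed.

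Fourth, simply changing V1-3 to V1-4 in the synopsis would go too far. That sentence also covers vital signs, ECG and laboratory tests, none of which the schedule marks at Visit 4. The fix has to avoid this.

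**Conclusion.** The inconsistency is certain on the text: one set of passages stops adverse-event assessment at day 14, another runs it through the whole study, and nothing reconciles them. Its size is 76 of 90 follow-up days (84.4%) in which no scheduled assessment elicits new adverse or serious adverse events.

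The consequence is unsystematic capture in that period, with possible differences between centres and between open-label arms. That rests on the assumption that centres may follow different passages. The protocol allows this but cannot show that it will happen. The documents do not support saying that the trial is blind to delayed events, and they give no basis for estimating how many would be missed or in which direction a comparison would move.

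The point should be corrected because safety is a stated objective, the remedy is small, and the data cannot be recovered afterwards.

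**What to change.** State one collection period for adverse and serious adverse events, with a start and an end, and make these places agree: the synopsis safety endpoint, the schedule of procedures, section 6 of the design, and Safety Evaluation sections 1 and 2.

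To match the whole-study rule that the protocol already contains:
- Mark the adverse-event row at Visit 4 in the schedule, and add it to the description of the final visit in section 6.
- Use a fixed set of questions at Visit 4: new events since day 14, rehospitalisation, and date and cause of death. Ask them identically in both arms.
- In the synopsis, leave vital-sign, ECG and laboratory monitoring at the visits already scheduled, and add only the adverse-event query at Visit 4.

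The cost is about one CRF page at a contact that already takes place, and some recall error over 76 days. No visit or test is added. The protocol does not say whether Visit 4 is in person or remote; the estimate assumes the questions can be asked either way.

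If the day-14 window was intended, section 6 and both safety sections should say so, and the safety objective and any safety conclusion should be limited explicitly to the 14-day treatment period.

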At V1 and V3, a routine brain MRI on a 1.5T scanner would be acquired followed by an axial DTI scan. The DTI sequence parameters are as follows: spin-echo echo-planar imaging, repetition time = 6000 ms, echo time = 102.9 ms, field of view = 260 mm, b-value = 0 and 1000 s/mm2, matrix = 256×256 ; slice thickness = 4.5 mm, interslice gap = 1 mm, total number of slices = 24, diffusion directions = 25, scan time = $5 \min 10$ s.

The maps of fractional anisotropy (FA), axial (AD), radial (RD) and mean (MD) diffusivity would be derived from the raw DTI scans.

At V3, a brain CT perfusion (CTP) scan would be obtained using the Dankbaar's approach. It involves a cine mode CT acquisition, with a temporal sampling rate of one image every 2 s for the first 60 s. Additional gantry rotations would be performed at 90, 120, 150, 180, 210 and 240 s. Acquisition parameters are 80 kVp and 100 mA. A bolus of 40 mL iohexol (Omnipaque, GE Healthcare, USA; 300 mg/mL of iodine) would be injected into an antecubital vein at an injection rate of 5 mL/s. CT scanning would be initiated 5 s after start of the injection of the contrast bolus. A series of CT scans covered the whole brain would be obtained with 5 mm slice thickness.

The CTP data would be processed to obtain a series of the permeability surface-area product (PS) maps.

The most representative slice would be chosen for analysis in each set of images. On that slice, the infarcted area is outlined and mirrored to the contralateral hemisphere. The values of FA, AD, RD, MD, and PS would be assessed within each region of interest.

To cope with the heterogeneity of the ischemic lesions due to different locations, absolute values of the laterality index for each parameter would be calculated using the formula:

|Laterality index| = (Affected side - Unaffected side) / (Affected side + Unaffected side) × 100%.

The infarct volume was calculated on DWI (at V1) and CT (at V3) scans according to the ABC/2 method [10].

Statistical methods

This statistical plan describes biostatistical analysis scheduled at the time of development of this study design. Detailed statistical analysis plan will be developed after study completion. Analysis report with final statistical analysis plan will be integral part of the clinical trial report.

Statistical analysis would be performed using statistical software like STATA, IBM SPSS Statistics.

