6. REFERENCE INFORMATION

Stroke is a severe disease and one of the leading causes of disability and lethality globally. Ischemic stroke (IS) accounts for the most part of stroke cases overall, i.e. up to 85 %. Reperfusion therapy is currently one of the verified effective IS treatment. IV TLT is deemed to be effective in improving neurological symptoms while reducing NIHSS by ≥ 4 within one day. One of the factors of reperfusion therapy failure may be reperfusion damage developing after recanalisation of a cerebral vessel and generally is considered as a consequence and progression of abnormal ischemic effects. Therefore, recanalisation of a clotted or embolised cerebral vessel within "therapeutic window" promotes preservation of the most part of inactive though viable neurons; meanwhile recovery of blood flow in ischemic area may cause reperfusion-induced cerebral tissue damage of various grades, thus aggravating peracute IS.

One of manifestations of reperfusion damage is BBB failure with increased permeability or impaired integrity resulting in exacerbation of edema of ischemic area or in hemorrhagic transformation (HT) of the ischemic area. Meanwhile, HTs are also reported without recanalisation effect and outside of the ischemia area; this is due to both cerebral tissue damage in hypoperfusion area and due to toxic effect of the thrombolytic agent. Thus, TLT increases the risk of HT 4-10-fold by activating matrix metalloproteinase 9, 2, 3 in neutrophils, endothelium, astrocytes, and platelet-derived growth factor-CC, however the pathogenesis of early (up to 24 hours) HTs and late HTs varies. While early HTs are associated with acute processes of BBB damage, the late ones are due to cerebral tissue inflammation and vascular remodelling. Clinically, the most relevant are symptomatic HTs (SHT) associated with aggravated neurological symptoms \geq 4 according to NIHSS scale or lethality (according to ECASS III 2008, 2016). Generally, SHTs have the nature of parenchymatous haematomas (hemorrhages, PH2 according to neuroimaging HT classification) exceeding 30 % at ischemic area. Smaller haematomas and petechia-like HTs are asymptomatic (HI-1, HI-2, PH-1).

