Development of the principles of pharmacological protection of cerebral tissue against reperfusion damage, one of the modifiable factors defining severity of cerebral damage and, therefore, neurological deficit and rehabilitation potential, is a promising trend in the treatment of acute cerebral ischemia.

Cerebrolysin has been approved for the treatment of stroke in more than 45 countries globally.

Significant progress has been made in stroke therapy since approval of cerebrolysin, including improved general care and condition of stroke units, rehabilitation became more targeted, fibrinolytic therapy (rt-PA, Actilise) - more commonly available in global specialised centers.

CLINICAL STUDY PURPOSES AND OBJECTIVES

The purpose of this study is to investigate the effect of cerebrolysin on post-reperfusion period in patients with ischemic stroke during thrombolytic therapy with decreased frequency of HTs. In addition, it is planned to study the hypothesis that cerebrolysin group will show better ischemic area and BBB changes, better general neurological status and functional outcomes.

CLINICAL STUDY DESIGN

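### The laterality index is described as an absolute value but printed as a signed ratio; taken as absolute, it loses direction, which matters most for PS

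*Protocol*

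**What the plan says.** The synopsis section on additional evaluation (advanced brain imaging) outlines the infarct on one slice, mirrors the region to the other hemisphere, and then: "The values of FA, AD, RD, MD, and PS would be assessed within each region of interest". The reason for an index is given as "To cope with the heterogeneity of the ischemic lesions due to different locations", and the rule follows: "absolute values of the laterality index for each parameter would be calculated using the formula". The formula has an opening bar before its first word, so the bars enclose only the left-hand side: "Laterality index| = (Affected side - Unaffected side) / (Affected side + Unaffected side) × 100" (a percent sign follows).

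The additional objective in the synopsis is to test whether Cerebrolysin would "ameliorate ischemic injury to the brain tissue (neuroprotective effect) and stabilize blood brain barrier (BBB) permeability in stroke patients". Section 6, Reference Information, names the direction of harm for the barrier: "BBB failure with increased permeability or impaired integrity". Under Clinical Study Purposes and Objectives, the expectation is only that the "cerebrolysin group will show better ischemic area and BBB changes".

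DTI is done at V1 and V3, CT perfusion (and so PS) at V3 only. The advanced imaging protocol under Efficacy Evaluation has the values in the region of interest and in the mirror reference area recorded for all five parameters.

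**The concern.** There are two problems. First, the rule contradicts itself. The sentence asks for an absolute value; the right-hand side of the formula is negative whenever the affected side reads lower. Two analysts could follow the same paragraph and produce different data, one signed and one not. The synopsis says that the detailed statistical analysis plan is to be written after study completion, so this paragraph is where the measure is defined beforehand.

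Second, if the sentence prevails, the sign is discarded. For PS the protocol says which direction is harmful, and the outcome measure could no longer show it. For the DTI parameters, a value that crosses from one side of zero to the other between V1 and V3 could appear unchanged. At stake is whether the imaging objective can tell a beneficial change from its opposite and, in some circumstances, how large a difference between the arms would appear.

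**Working it through.** **Inputs.** From the protocol: the formula, the five parameters, the visits and the stated direction of harm for PS. The protocol gives no mean, SD, effect size or sample size for the index, so there is no figure of its own to reproduce. The numbers in steps 3 and 4 rest on assumptions: a normally distributed signed index and, in step 3, the same SD in both arms.

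**1. The formula and the loss of sign.** With A the affected and U the unaffected side, LI = (A − U)/(A + U) × 100%.

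- A = 0.6, U = 0.4: LI = +20%, |LI| = 20%.
- A = 0.4, U = 0.6: LI = −20%, |LI| = 20%.

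In the second case the two sides of the printed equation differ (20% against −20%). For PS, the two cases are a rise and an equal fall relative to the mirror side, and |LI| scores them alike. For a DTI parameter, a move from −20% at V1 to +20% at V3 is a signed change of 40 points and a change in |LI| of 0.

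**2. Is the absolute value needed for lesion location?** Subtracting unaffected from affected already makes the index independent of which hemisphere is involved. Dividing by the sum already scales it to the tissue at that location. Removing the sign adds nothing to either.

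**3. Effect on an arm difference.** For a normal index with mean m and SD s:

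E|LI| = s·√(2/π)·exp(−m²/2s²) + m·(1 − 2Φ(−m/s))

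Var|LI| = m² + s² − (E|LI|)²

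Worked for means of 1.0 and 0.5 with s = 1: E|LI| = 0.484 + 0.683 = 1.167 and 0.704 + 0.191 = 0.896. The difference is 0.271 against a signed difference of 0.5, so 54% is kept and 46% lost. The SDs of |LI| are 0.799 and 0.669 (pooled 0.737), so the standardised effect is 0.271/0.737 = 0.368, or 74% of 0.5.

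The same calculation for a signed difference of 0.5 SD at other positions:

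| Arm means (SD units) | Share of patients below zero | Mean difference kept | Standardised effect kept |
|---|---|---|---|
| 3.0 / 2.5 | 0.1% / 0.6% | 99% | 100% |
| 2.5 / 2.0 | 0.6% / 2.3% | 97% | 99.6% |
| 2.0 / 1.5 | 2.3% / 6.7% | 92% | 98% |
| 1.5 / 1.0 | 6.7% / 15.9% | 78% | 92% |
| 1.0 / 0.5 | 15.9% / 30.9% | 54% | 74% |
| 0.5 / 0 | 30.9% / 50% | 20% | 31% |
| 0.25 / −0.25 | 40.1% / 59.9% | 0% | 0% |

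With equal SDs the difference in mean |LI| cannot exceed the signed difference, because the slope of E|LI| in m is 1 − 2Φ(−m/s), which is below 1 in size.

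**4. Unequal SDs.** With both means at 0, E|LI| = s·√(2/π). SDs of 10 and 15 points give 8.0 and 12.0: a gap of 4 points in mean |LI| where the signed means are equal.

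**The case against.** The strongest defence is that |LI| measures distance from the healthy side. No expected sign is stated for FA, AD, RD or MD, so for these it is a coherent summary of injury, and a signed index does not by itself say which sign is better. This stands, and it is a reason to keep |LI| as a supplement. It is weaker for PS, where the protocol names increased permeability as the harm.

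The patients imaged may also lie far from zero. They need a diffusion lesion of at least 20 mm, the region measured is the outlined infarct, and the slice is the one with the largest changes. This selects for marked asymmetry, and if nearly all values fall on one side the numerical loss is negligible. It makes large losses less likely but does not exclude them, since no mean or SD is given.

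The consequence is also limited. Imaging is an additional objective for eligible patients at the tertiary center, the whole analysis is declared exploratory, and the raw values are kept, so nothing is irrecoverable. The protocol states no specific test of |LI|. All of this stands and lowers the weight of the point.

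A reader might infer more than the text supports:

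- *That the absolute value always shrinks true differences.* The loss depends on where the arms lie, and unequal SDs can work the other way.
- *That it requires a larger sample by some fixed factor.* No imaging sample size or power is stated, so any factor would come from a chosen scenario.
- *That a working treatment moves patients towards zero, where the loss is greatest.* The documents do not say so, and the measurement is taken inside the infarct.
- *That PS could change sign between visits unnoticed.* PS is measured only at V3.

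**Conclusion.** The point holds in a limited form. Without any assumption: the sentence and the formula disagree whenever the affected side is lower; the absolute value is not needed for the stated purpose; and, if used, it makes a PS rise indistinguishable from an equal fall and can hide a sign change in a DTI parameter. No passage says that such a sign change occurs; the measure simply could not show it.

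The numerical distortion is conditional. Under a normal index with equal SDs it runs from negligible to complete, and the documents do not show where this trial falls. A documented direction exists for PS only, so the claim that the rule defeats a stated direction should not be extended to all five parameters. The primary and secondary endpoints are unaffected. This is a self-contradictory definition in an exploratory measure, worth correcting because the correction is nearly free.

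**What to change.** - Correct the formula so that label and expression agree: LI = (affected − unaffected)/(affected + unaffected) × 100%, without bars.
- Make the signed index the main measure for PS at V3.
- For FA, AD, RD and MD, report the signed index at V1, at V3 and for the change, and state the expected sign for each parameter beforehand.
- Keep |LI|, with bars on both sides of its own formula, only as a supplementary measure of distance from the healthy side.

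The cost is a short text change. No new scans or data fields are needed, because the values on both sides are already to be recorded for all five parameters.
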